7.9. Enrollees May Drop Out

Participants and/or their LARs may voluntarily withdraw from participation at any time, for any reason, with no penalty or loss of rights, or indicated treatment. The reasons for drop-out and missing data will be documented in the database. Drop-out from the study during the intervention phase will probably not imply patients leaving the hospital because of the intervention's short time frame and the target population's characteristic clinical condition. For those cases, we will schedule a personal interview between the research team and the LAR to solve doubts if the LAR accept by phone call. No efforts will be made to follow up with patients who drop out after the follow-up tests were taken because, after that time, the data collected is not relevant for the major outcomes of interest.

8. Statistical Analysis Plans

8.1. Strategies that Apply to all the Aims

All statistical procedures will be performed in SAS and R. Biostatistician [name] will oversee all data analyses.

- (i) All data will be scored and rescored by separate staff members and checked for accuracy prior to double entry into our database. All datasets are backed up daily.

- (ii) Prior to statistical modeling, we will perform descriptive analyses and data visualizations to examine the distributions of all measures. Appropriate transformations to obtain approximate normality will be performed; where necessary, additional nonparametric tests will confirm results.
- (iii) Linear regression model and nonparametric tests (e.g., Wilcoxon rank sum test) will be the primary analytic tools for testing our *a priori* hypotheses. Model selection methods (e.g., Bayesian information criterion) and sensitivity analysis methods will be used to select models and assess various model assumptions. We will consider the use of appropriate covariates as detailed below in all aims.
- (iv) We will record the reasons for drop-outs, missing / censored data values, and protocol departures in the database. We will appropriately handle drop-outs and missing data (e.g., missing responses and/or covariates) by using imputation or other estimation methods (e.g., missing completely at random), while considering anticipated causes. We will carry out sensitivity analysis to evaluate different missing mechanisms.
- (v) We will use test statistics (e.g., likelihood ratio test) to test the hypotheses. To identify significant component terms in each of the models, we will examine the parameter estimates, 95% confidence intervals, and p-values of the component terms in an analysis of fixed effects for the final regression models. All statistical estimates of population parameters will be tabulated along with corresponding confidence intervals (CIs) and/or standard errors (SEs) to convey levels of precision / imprecision.

We will use graphical methods such as forest plots to visualize the analysis results. We will also include outcome-dependent exploratory analyses to generate new hypotheses.

8.2. Sample Description

We will use graphical figures (e.g., forest plots with tabulations, scatter plots, histograms, box-and-whisker plots, etc.) and descriptive statistical methods to describe the sample of individuals studied; they include graphical figures, counts, frequencies, sample means, sample standard deviations, percentiles, min, max, and standardized differences.

We will compare SzNET+/EEG+ with SzNET+/EEG- in terms of baseline/pre-treatment characteristics.

8.3. Aim-Specific Plans

Plans for Aim 1.

Aim 1 is to obtain preliminary data about the degree of improvement of seizure networks (SzNET) in moderate to severe acute brain injury (MSABI) patients after intervention's antiseizure medication (ASM).

Aim 1a

Measure the improvement of the SzNET total volume in MSABI patients after the intervention's ASM. The primary outcome of interest is the SzNET total volume median before and after the intervention's ASM in the target population.

H_0 : there will be no difference in the SzNET total volume median in MSABI patients before and after the intervention's ASM.

H_1 : SzNET total volume median in MSABI patients before ASM will be smaller than after the intervention's ASM.

Aim 1b

Measure the improvement of the SzNET power spectrum in MSABI patients after ASM. The outcome of interest is the SzNET power spectrum median before and after ASM in the target population.

H_0 : there will be no difference in the SzNET power spectrum median in MSABI patients before and after the intervention's ASM.

H_1 : SzNET power spectrum median in MSABI patients before ASM will be higher than after ASM.

We plan to recruit 11 patients with SzNET+EEG+ and 11 subjects with SzNET+EEG-. Therefore, 22 subjects with measurements before and after the intervention's ASM will be used in Aims 1a and 1b. We will fit linear regression models with dependent variables as follows. We calculate the changes of the SzNET total volume and the SzNET power spectrum before and after the intervention's ASM and use them as the primary dependent variables. Due to the small number of subjects, we only include an intercept to represent the mean difference before and after the intervention's ASM in the model, and we use the t-test statistic to test whether the intercept is equal to zero for Aims 1a and 1b. Moreover, we may consider demographic variables and pre-intervention EEG status (EEG+ or EEG-) if necessary.

Plans for Aim 2.

Estimate the frequency of EEG- and EEG+ patients presenting SzNET. The outcomes of interest are the proportions and differences of proportions of patients with SzNET among EEG- and EEG+ patients in this clinical setting.

For aim 2, we sequentially recruit SzNET+ subjects until the number of subjects in either SzNET+EEG+ or SzNET+EEG-first reaches 11 subjects. We will calculate the proportions of patients with SzNET among EEG- and EEG+ patients. and use the two-proportion Z-test to test their difference.

Plans for Aim 3.

Investigate association between post-intervention EEG improvement and SzNET response. The outcome of interest is the relative risk of EEG improvement in patients with more than 50% improvement of their SzNET by TVR and PSI.

H_0 : there will be no difference in the EEG improvement between the patients with and without more than 50% improvement of their SzNET.

H_1 : EEG improvement will be greater in the patients with more than 50% of SzNET improvement.

There are 22 subjects used in Aim 3. We will fit logistic regression model to characterize the association between the EEG improvement with the patients with and without more than 50% improvement of either PSI or TVR. We will use the Wald test and likelihood ratio test statistics to test the null and alternative hypotheses.

Plans for Aim 4.

Investigate association between the post-intervention typical resting state networks (RSN) connectivity improvement and the SzNET response. The outcome of interest is the relative risk of improvement of the typical RSN in the patients with more than 50% of improvement of their SzNET by TVR and PSI.

H_0 : there will be no difference in the typical resting state networks connectivity improvement between the patient with and without more than 50% improvement of their SzNET.

H_1 : Median typical resting state networks connectivity improvement will be greater in the patients with more than 50% of SzNET improvement.

There are 22 subjects used in Aim 4. We will fit logistic regression model to correlate the RSN improvement with the patients with and without more than 50% improvement of either PSI or TVR and use the Wald test and likelihood ratio statistics to test the null and alternative hypotheses.

Plans for Aim 5.

Describe psychosocial functional measure outcomes and ambulatory ASM toxicity at 3 months from discharge. The outcomes of interest will be the PROMIS Emotional Distress—Anxiety— Short Form, the Neurological Disorders Depression Inventory for Epilepsy (NNDI-E), the QOLIE-10-P, the Telephonic Montreal Cognitive Assessment, and the Liverpool adverse event profile test. All will be assessed at the 3 month follow-up visit to one of the NSICU Post-Discharge clinics.

Plans for Aim 6.

Aim 6 is to assess the trial's design feasibility success in enrollment and retention by evaluating the enrollment rate and dropout rate among participants at the end of the trial.

Aim 6a

Measure the enrollment during all the months of study enrollment. The primary outcome of interest is the rate of monthly enrolled patients.

Aim 6b

Measure the participants dropout among participants during the study. The primary outcome of interest is the dropout rate among the total number of enrolled participants at the end of the study.

We will calculate the summary statistics of these measurements.

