SICU	Surgical intensive care unit
SOC	Standard of care
SOM	School of Medicine
SOP	Standard operating Procedures
SzNET	Seizure networks defined by resting state functional MRI
SzNET-	That has presence of Seizure networks observed in resting state functional MRI #1
SzNET+	That has presence of Seizure networks observed in resting state functional MRI #1
TE	Echo time
T-MoCA	Telefonic Montreal Cognitive Assessment
TR	Repetition time
TraCS	N.C. Translational and Clinical Sciences Institute (tracs.unc.edu)
TV	Total volume
TVR	Total volume reduction
UNC	The University of North Carolina
UNCH	UNC Hospitals
UP	Unanticipated Problem

1. Protocol Synopsis

Title	Resting state fMRI BOLD Offers Opportunity for Treatment in Coma
Study Description	This is an open-label pilot clinical trial in the PICU, NSICU, SICU, CTICU, CICU, and MICU at UNCH to characterize the behavior of Seizure Networks (SzNET) in 18 months to 70 years old patients with moderate to severe acute brain injury (MSABI) and suppression of consciousness. It will assess the reduction of SzNET after antiseizure medication (ASM) using pre/post-treatment rs-fMRI and compare that response to EEG and normal resting state networks (RSN).
Specific Aims (objectives)	Aim 1. Estimate the degree of improvement of SzNET in MSABI patients after intervention. Aim 1a. Measure the improvement of the SzNET total volume in MSABI patients after the intervention. Aim 1b. Measure the improvement of the SzNET power spectrum in MSABI patients after the intervention.

	
Aim 2. Estimate the proportion of EEG- and EEG+ patients presenting SzNET on the initial rs-fMRI.
 
Aim 3. Investigate association between pre/post-intervention EEG improvement and SzNET response.
 
Aim 4. Investigate the association between the intervention responses of the normal resting state network connectivity and the SzNET in MSABI patients.
 
Aim 5. Describe psychosocial functional measure outcomes and ambulatory ASM toxicity at 3 months from discharge.
 
Aim 6. Assess the trial's design success regarding participants enrollment and retention.
 
Aim 6a. Measure the enrollment rate.
 
Aim 6b. Measure the dropout rate.

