- The presence of SzNET will classify the patients that will receive intervention corresponding to the protocol and those that will only continue medical treatment according to care team indications in case of the presence or the absence of SzNET in the first MRI, accordingly. Outcomes will be reported as proportions and differences of proportions of patients with SzNET among EEG- and EEG+.
- Surface EEG monitoring pre-intervention (Seizures) is a binary variable collected from the total available surface EEG monitoring before rs-fMRI#1 with EEG+ and EEG- as possible values and retrieved by the investigators from the medical record or direct communication with the Epileptologist, which later must be supported in the medical records. EEG+ is defined as surface EEG with the presence of electrographic seizure, electroclinical seizure or ictal-interictal continuum.

Outcome Variables:

Each SzNET is made of one or more BOLD signal independent components that share atypical temporal or spatial features ¹¹.

- SzNET total volume (TV) is the sum of the volumes of the SzNET independent components. The TV change from before to after the intervention is a ratio expressed as the TV reduction (TVR), and is given by:

$$TVR = 1 - \frac{\sum_{i=1}^n P_i}{\sum_{i=1}^n E_i}$$

Where P is the volume of a post-treatment SzNET, E is the spatial volume of an initial SzNET and n is the amount of SzNET in each rs-fMRI.

- Power Spectrum (PS) is the sum of the power spectrum of the SzNET independent components normalized by their spatial volumes. The PS change from before to after the intervention is a ratio expressed as the PS improvement (PSI) and is given by:

$$PSI = 1 - \frac{\sum_{i=1}^n [P \int_{6.78}^{27.12} f(s)]_i}{\sum_{i=1}^n [E \int_{6.78}^{27.12} f(s)]_i}$$

Where F(S) is the power spectrum curve.

- EEG improvement Binary variable categorized in "with improvement" or "without improvement", obtained by expert's overall qualitative assessment comparing the follow-up study EEG and the clinically indicated EEG considered at the enrollment time. This qualitative assessment will be based on the EEG's background and the presence of electrophysiological signs of ictal or interictal activity.

These signs are described by the American Clinical Neurophysiology Society as:

- o Epileptiform Discharges
- o Rythmic and periodic patterns
- o Electrographic and electroclinical seizures.
- o Ictal-interictal continuum.

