8.4. Planned Interim Analyses

No interim analyses will be performed.

9. Sample Size Rationale

There is no preliminary data for effect size estimation using the paradigm and patient population suggested in this study. In Aim 1, a paired t-test is used to test measurement differences before and after ASM. A effect size 0.806 can be detected for a 1-sided test at a power of 80% and a Type I error at 0.05 with the total of 11 subjects before and after ASM. In Aim 4, a transformed Z-test is used to test correlation between two variables. A correlation size 0.506 can be detected for a 1-sided test at a power of 80% and a Type I error at 0.05 with the total of 22 subjects.

10. Data Capture and Database Management

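### The alternative hypothesis for primary Aim 1a points the wrong way under a one-sided design, and Section 9's 11 subjects are not the 20 to 22 in the planned test

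*Combined protocol and SAP*

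**What the plan says.** **Direction.** For Aim 1a, Section 8.3 gives the alternative hypothesis as "SzNET total volume median in MSABI patients before ASM will be smaller than after" the intervention. The Aim 1b alternative a few lines later runs the other way: "SzNET power spectrum median in MSABI patients before ASM will be higher than after ASM". The synopsis says of the study: "It will assess the reduction of SzNET after antiseizure medication (ASM"). Section 4.3 says "The TV change from before to after the intervention is a ratio expressed as the TV reduction (TVR"), with the formula 1 minus post-treatment volume over initial volume. That quantity is positive only when volume falls.

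**Test.** Section 8.3 fits an intercept-only model to the before-after changes and will "use the t-test statistic to test whether the intercept is equal to zero for Aims 1a and 1b". It names no tail. Section 9 describes the Aim 1 test as a paired t-test and says "A effect size 0.806 can be detected for a 1-sided test at a power of 80"%, with type I error 0.05.

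**Number of subjects.** Section 9 attaches that figure to a sample "with the total of 11 subjects before and after ASM". Section 8.3 instead plans Aims 1a and 1b on "22 subjects with measurements before and after" treatment, pooling 11 EEG+ and 11 EEG- patients. Section 5.1 expects 20 of the 22 treated patients to complete therapy and the repeat scan, 10 in each stratum. Section 7.8 limits the data of dropouts to Aim 2.

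**The concern.** Total volume and its reduction are listed as primary outcomes in the variables table of Section 4.3. A one-sided test takes its rejection region from the alternative hypothesis. Here the only statement of sidedness (Section 9) and the only statement of direction for volume (the Aim 1a hypothesis) together put that region in the tail for growth. A treatment that shrinks the networks could then not produce a significant result. Section 2.2 says that further work relating the networks to outcome may be unnecessary if they show no significant change, so the result of this test has consequences.

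The mismatch in n is a separate and lesser matter. The only detectable effect that the plan gives for Aim 1 belongs to a sample half the size of the planned one, so a reader cannot tell what the planned analysis could detect.

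**Working it through.** **Inputs.** Paired t-test, alpha 0.05, power 80%, detectable effect 0.806 and n = 11 (Section 9); n = 22 pooled (Section 8.3); n = 20 completers and 10 per stratum (Section 5.1). A reduction of 0.5 SD is an assumption, added to show a smaller effect. Effects are in units of the SD of the within-patient change.

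**Formulae.** Let D = after minus before, T = mean(D) / (SD(D)/√n), with n - 1 degrees of freedom. For a true reduction of d, put λ = d√n, and let T'(λ) be noncentral t with n - 1 degrees of freedom.

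- Intended one-sided power: P(T'(λ) > t at 0.95).
- One-sided power with the alternative as written: P(T'(-λ) > t at 0.95).
- Two-sided power: P(|T'(λ)| > t at 0.975).

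**Step 1: reproduce Section 9.** With n = 11, the critical value is 1.812 and λ = 0.806 × √11 = 2.673. One-sided power is 0.7999, and solving for 80% gives d = 0.8061. The plan's 0.806 is therefore right for 11 subjects, one-sided.

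**Step 2: effect of the reversed direction.** With n = 20 and d = 0.806, λ = 0.806 × √20 = 3.605 and the one-sided critical value is 1.729.

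| True reduction | n | One-sided, as written | One-sided, intended | Two-sided |
|---|---|---|---|---|
| 0.806 SD | 20 | 1.5e-7 | 0.966 | 0.927 |
| 0.806 SD | 22 | 5.4e-8 | 0.978 | 0.950 |
| 0.5 SD (assumed) | 20 | 7.1e-5 | 0.695 | 0.565 |

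The third row shows that sidedness matters even once the direction is right: the power differs by 0.695 - 0.565 = 0.13.

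**Step 3: detectable effect at 80% power for each candidate n.**

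| n | Where it comes from | One-sided | Two-sided |
|---|---|---|---|
| 10 | completers per stratum, Section 5.1 | 0.853 | 0.996 |
| 11 | Section 9 | 0.806 | 0.938 |
| 20 | pooled completers, Section 5.1 | 0.577 | 0.660 |
| 22 | pooled, Section 8.3 | 0.548 | 0.626 |

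On the one-sided scale, Section 9's figure is 0.806/0.577 = 1.40 to 0.806/0.548 = 1.47 times the effect that the pooled test can detect. If 11 was meant per stratum, Section 8.3 has no stratum-specific Aim 1 test to go with it. With the 10 completers expected per stratum, one-sided power at 0.806 is 0.76, not 0.80.

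**The case against.** The near-zero power needs two passages to be combined that the plan does not itself combine. The instruction for the analysis, in Section 8.3, is to test the intercept against zero. Read as two-sided, it detects a reduction whatever the hypothesis says. Section 8.1 also calls for estimates, 95% confidence intervals and p-values, and the estimates and intervals do not depend on the hypothesis wording. Section 3.1 presents Aim 1 chiefly as estimation of a magnitude. The intended direction is plain from everything else, so a wrong-tail analysis is unlikely.

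On n, the error is conservative, and the enrolment target does not rest on it: Section 5.1 derives 22 from 10 completers per stratum plus attrition. Eleven is also each stratum's quota, so an unlabelled per-stratum figure is a plausible reading. The analysed n is not fully settled either, since Section 8.1 mentions imputation for dropouts and Section 5.1 allows recruitment to continue after Aim 2 until the strata are filled.

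Most of this stands, and it limits the practical harm. It does not make the text right. No passage corrects the Aim 1a hypothesis, and no passage states that the test is two-sided. The one place that gives a side says one-sided. A choice of tail left open until the data are seen would be a post hoc choice on a primary outcome. As for n, neither the pooled nor the per-stratum reading makes Section 9 agree with Section 8.3.

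**Conclusion.** The plan is wrong as written on both counts. The Aim 1a alternative contradicts the study's purpose, its own outcome definition and its companion hypothesis. This must be corrected because it is a primary hypothesis and Section 9 assumes a one-sided test. The power of about 1.5e-7 at n = 20 is conditional: it applies only if the written direction and Section 9's one-sided test are used together. Under a two-sided test the reversal has no effect on the p-value, and power for 0.806 SD is 0.927.

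The mismatch in n is the lesser part. Section 9's arithmetic is correct for 11 subjects but does not describe the planned pooled test, whose detectable effect is 0.548 to 0.577 one-sided or 0.626 to 0.660 two-sided. The study is not underpowered because of it. These figures assume approximately normal within-patient changes and an analysed sample of 20 to 22.

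**What to change.** 1. In Section 8.3, reword the Aim 1a alternative so that total volume before ASM is larger than after, matching Aim 1b.
2. State in Sections 8.3 and 9 whether the Aim 1a and 1b tests are one-sided or two-sided, using the same choice in both places. If one-sided, define the sign of the change so that the rejection tail is explicit.
3. In Section 9, say which n the detectable effect refers to and restate it: 0.577 one-sided or 0.660 two-sided for 20 completers, or 0.548 or 0.626 for 22. If 11 was meant per stratum, label it so, add the stratum-specific test to Section 8.3, and give the figure for 10 completers (0.853 or 0.996).

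The cost is one word, one phrase on sidedness and one sentence in Section 9; the per-stratum option also needs a short addition to Section 8.3. No patients, procedures or data are added.

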2.2. Scientific Rationale

Study Proposal: This is an uncontrolled two-arm open-label single-center interventional clinical trial that will be used to prepare for a full-scale randomized, placebo-controlled trial by investigating the feasibility of the study and proposed measures collection. It will explore changes in SzNET, RSNs, and EEG data, before, and after combination drug therapy with levetiracetam and phenobarbital (or a combination of two other ASM drugs (see section 4.1) and psychometric measures at 3 months after hospital discharge based on a sample of 54 patients with MSABI and DoC. Our long-term goal for this research line is to determine if SzNET are linked to epileptogenic activity in SABI to improve the endotype characterization of its DoC and better guide targeted treatments.

Rational for specific aims and outcome measures: The purpose of this study is to determine the occurrence of a specific biomarker called SzNET in patients with MSABI and investigate the effects of ASM on SzNET. The study also aims to find any correlation between EEG and SzNET in patients who experience seizures on EEG.

The study outcome measures will focus on quantifiable changes in SzNET and RSNs with therapy. It is difficult to isolate the effects of early therapy on outcomes due to the high rate of withdrawal of life sustaining therapy in the early weeks of MSABI and the potential secondary injuries. Therefore, this study will take a conservative approach and focus on quantifiable changes in SzNET and RSNs with therapy. If there are no significant changes in the networks after therapy, it may not be necessary to further investigate the relationship between SzNET and outcomes. The feasibility of collecting outcomes and trends in relation to SzNET will be tested as part of this pilot study through ICU exams and follow-up clinics, including side effects of medication, morbidity, and mortality, to identify any positive trends.

Rational for study inclusion/exclusion criteria: This study focuses on patients with brain damage severe enough to impair consciousness but with the potential to recover in the absence of epileptogenic activity. The inclusion criteria have been chosen to identify patients with this level of brain damage.

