Restated: Seizure network activity could be the cause of suppressed conscious in acute brain injury. The EEG, which is the best current test for detection of seizure, may not detect this activity, if it is occurring in deep brain locations. SzNET by rs-fMRI may be a biomarker of abnormal activity in acute brain injury that could be responsive to ASM. In ICU patients with suppression of consciousness, we will use the EEG to stratify patients into two groups, EEG+ and EEG-. EEG+ will be defined by either electrographic seizure, electroclinical seizure or ictal-interictal continuum as defined by the American clinical Neurophysiology Society's Standardized Critical Care EEG Terminology²⁸, whereas EEG- will be lacking these features. Further, we will observe the rate of SzNET by rs-fMRI in both groups, and response of the SzNET and EEG to study intervention.

To ensure rapid recruitment, the study will use a quota sampling strategy. Specifically, eleven SzNET+ patients will be recruited consecutively for each EEG+ and EEG- strata to ensure the necessary number of patients for the interventional phase of the study.

Data collection

First, informed consent will be obtained from the subject's legally authorized representative (LAR). Then, baseline variables will be collected by interview and review of medical charts. After subjects are scanned, the rs-fMRI images are uploaded to the UNCH MRI PACS system by an MRI technician and accessed through the UNCH secure PACS portal by study personnel, through download onto the UNC SOM secure system. There, the rs-fMRI processing and analysis are accomplished, and information is deidentified for storage in the PI's UNC-OneDrive. Clinical and demographic data will be collected by the study research coordinator and stored in a REDCap file. Once the study data collection is completed, the deidentified REDCap database will be used for analysis and stored at the PI's UNC-OneDrive. A separately stored subject key code in a SOM-stored research excel file will link the research subject's codes and MRN until five years after study completion. Hospital discharged patients will be followed through one of the NSICU Post-Discharge clinics, and that data will be stored in the same study REDCap file.

End-of-study criteria and discontinuation criteria for the participant.

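### Aim 3 tests EEG improvement against SzNET response in one pooled model and does not commit to using EEG status, the quota stratum, so a difference between strata could pass for an association.

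*Combined protocol and SAP*

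**What the plan says.** **Model.** Section 8.3, Plans for Aim 3, says "There are 22 subjects used in Aim 3". It fits a logistic regression of EEG improvement comparing "patients with and without more than 50% improvement of either PSI or TVR". On testing: "We will use the Wald test and likelihood ratio test statistics to test the null and alternative hypotheses". No EEG-status term, stratum or subgroup is named. The estimand, here and in Section 3.3, is a relative risk, and the alternative hypothesis is directional.

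**Who the 22 are.** Sections 5.5 and 8.3 fix them by quota at 11 EEG+ and 11 EEG- patients, all SzNET+.

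**Outcome.** Section 4.3 defines EEG improvement as an expert's overall yes/no rating: "This qualitative assessment will be based on the EEG's background and the presence of electrophysiological signs of ictal or interictal activity". Four signs are listed: epileptiform discharges, rhythmic and periodic patterns, seizures, and the ictal-interictal continuum.

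**Stratum.** Section 4 (rationale for stratification by EEG) defines EEG+ by seizures or the ictal-interictal continuum, "whereas EEG- will be lacking these features".

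**Where EEG status appears in the analysis.** Section 8.3 makes it an optional covariate for Aim 1. Table 2 of Section 4.3 lists it for all aims, in the role of classification. Section 8.1(iii) says suitable covariates will be considered as set out under each aim; Aim 3 sets out none.

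**The concern.** Two of the four listed signs are the ones that separate the strata. In an EEG+ patient, improvement can mean that seizures or the ictal-interictal continuum resolved. In an EEG- patient it can only mean a change in background, discharges or rhythmic and periodic patterns. The chance of being rated improved may therefore depend on the stratum.

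If the chance of an SzNET response also depends on the stratum, EEG status is a common cause of both variables. A pooled model would then report an association between SzNET response and EEG improvement even if the two were unrelated among EEG+ patients and among EEG- patients. The pilot is meant to inform a larger trial in EEG-, SzNET+ patients, so an association produced by the contrast between strata would be misleading evidence for that trial.

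**Working it through.** **Inputs from the documents**
- Planned for Aim 3: 11 + 11 = 22, which reproduces the stated number.
- Expected completers: Section 5.1 allows for attrition of 1 in 10 and needs 10 + 10 = 20. Section 7.8 uses dropouts for Aim 2 only. The check therefore uses 10 per stratum.
- Significance level: none is stated for Aim 3. Section 9 uses one-sided 5% for Aims 1 and 4. Both sidednesses are shown.

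**Inputs assumed.** The documents give no rates by stratum. Let *r* be the probability of an SzNET response above 50% and *e* the probability of EEG improvement, with subscripts + and - for the strata. Within each stratum the two are taken as independent, so any rejection is a false positive.

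**Formula.** With equal strata the pooled cell probabilities are

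- a (response, improved) = (r₊e₊ + r₋e₋)/2
- b (response, not improved) = (r₊(1−e₊) + r₋(1−e₋))/2
- c (no response, improved) = ((1−r₊)e₊ + (1−r₋)e₋)/2
- d (neither) = ((1−r₊)(1−e₊) + (1−r₋)(1−e₋))/2

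and ad − bc = (r₊ − r₋)(e₊ − e₋)/4. The pooled association is zero unless *both* differences are non-zero, and its sign is the sign of their product.

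**Milder case:** r = 0.70/0.50, e = 0.70/0.30 (EEG+/EEG-).
- a = (0.49 + 0.15)/2 = 0.32; b = (0.21 + 0.35)/2 = 0.28; c = (0.21 + 0.15)/2 = 0.18; d = (0.09 + 0.35)/2 = 0.22
- Pooled relative risk = (0.32/0.60)/(0.18/0.40) = 1.19; odds ratio = (0.32 × 0.22)/(0.28 × 0.18) = 1.40

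**Stronger case:** r = 0.80/0.40, e = 0.80/0.20.
- a = (0.64 + 0.08)/2 = 0.36; b = (0.16 + 0.32)/2 = 0.24; c = (0.16 + 0.12)/2 = 0.14; d = (0.04 + 0.48)/2 = 0.26
- Pooled relative risk = (0.36/0.60)/(0.14/0.40) = 1.71; odds ratio = (0.36 × 0.26)/(0.24 × 0.14) = 2.79

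**Reversed case:** r = 0.40/0.70, e = 0.80/0.20. Here ad − bc = (−0.30)(0.60)/4 = −0.045, and the pooled odds ratio is 0.48.

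**Error rates.** All pairs of 2x2 tables with 10 per stratum were enumerated. The pooled likelihood ratio test was compared with a Mantel-Haenszel test stratified by EEG status (large-sample form, no continuity correction).

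| Assumed rates (r; e, EEG+/EEG-) | Pooled, one-sided 5% | Pooled, two-sided 5% | Stratified, one-sided 5% |
|---|---|---|---|
| Identical strata, all 0.50 | 6.1% | 5.8% | 4.9% |
| Equal response 0.50; 0.70/0.20 | 6.1% | 5.7% | 4.8% |
| 0.70/0.50; 0.70/0.30 | 11.9% | 7.8% | 5.2% |
| 0.80/0.40; 0.80/0.20 | 33.1% | 21.5% | 5.6% |
| Reversed: 0.40/0.70; 0.80/0.20 | 0.9% | 13.8% | 2.9% |

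The first row matters: the pooled test is already near 6% at this sample size for reasons unrelated to pooling. The excess due to pooling is therefore about 6 points one-sided (11.9 − 6.1) and 2 points two-sided (7.8 − 5.8) in the milder case, and 27 points one-sided (33.1 − 6.1) in the stronger one.

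**Price of stratifying when it is not needed.** With an assumed odds ratio of 6 inside each stratum, 50% response and 50% improvement in both, and 10 per stratum, one-sided power is about 63% pooled and 57% stratified.

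**The case against.** **Adjustment is already allowed.** A reader might infer that EEG status plays no part outside Aim 1. That is not so: Table 2 of Section 4.3 lists it for all aims, and Section 8.1 provides for covariates, model selection and sensitivity analysis. This stands. What remains is that nothing commits Aim 3 to using it.

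**The bias is conditional, and the pilot does not show the condition.** Table 2 of Section 2.1 (six treated patients) reports SzNET improvement in 100% with 60% EEG-, so response did not differ by stratum. This stands, with limits: the sample is tiny and uncontrolled, the table does not say that it used the 50% threshold, and 60% of six is 3.6 patients, so that row's denominator is unclear.

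**Section 4.1 does not predict a lower response in EEG- patients.** It contrasts epileptogenic networks with networks of other origin, not EEG+ with EEG-. The protocol's premise is that SzNET in EEG- patients may reflect activity that scalp EEG misses, which could give similar response in both strata. A difference is plausible but not stated.

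**Including EEG- patients is deliberate.** Two stronger readings are tempting. One is that EEG- patients cannot improve; Section 4.3 rules this out, since background, discharges and rhythmic or periodic patterns also count. The other is that Aim 3 should be confined to EEG+ patients because Section 2.2 says "The study also aims to find any correlation between EEG and SzNET in patients who experience seizures on EEG". That sentence is general rationale. Sections 3.3 and 8.3 define Aim 3 without such a limit, and Section 4 plans to observe SzNET and EEG response in both groups.

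**A stratified relative risk still averages outcomes of different meaning.** This is fair, and is why the two tables should also be shown separately.

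**Conclusion.** The point holds as a cheap improvement to a secondary aim of a pilot. The plan specifies an unadjusted pooled analysis across a stratum that bears on what its outcome can mean, and it permits but does not commit to accounting for that stratum.

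Under the assumed rates, the one-sided error of the pooled likelihood ratio test is about 12% to 33%, against about 6% with identical strata and 5% to 6% when stratified. These figures rest on 10 completers per stratum, no association within strata, a one-sided 5% level that the plan does not state for Aim 3, and gaps between strata of 20 to 40 points in SzNET response and 40 to 60 points in EEG improvement. With equal SzNET response, pooling adds no bias. With the difference reversed, pooling pulls the estimate below 1 and can hide a real association.

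A reader might infer that Aim 3 will wrongly support SzNET as an epileptogenic marker. The documents do not support that: they give no stratum rates, and the only pilot data show no difference in SzNET response. What is established is the omission, not the presence of bias.

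**What to change.** In Section 8.3, Plans for Aim 3, commit to one of two analyses using pre-intervention EEG status:

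1. a Mantel-Haenszel relative risk stratified by EEG status, with an exact stratified test; or
2. the planned logistic model with EEG status as a fixed term.

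The first estimates the stated estimand, a relative risk, directly. Keep both strata in Aim 3, and report the EEG+ and EEG- 2x2 tables separately as descriptive results.

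**Cost.** SAP wording only; EEG status is already collected and is the quota stratum. If there is no confounding, power falls modestly (about 63% to 57% in the example, and normally somewhat further with an exact test). Intervals within strata of about 10 patients will be wide, which is why those tables should be read as descriptive.
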